The specific hypotheses of the present study were as follows: (a) There will be significant differences in the adherence to treatment, being higher in the ENTREN-F group (b) There will be improvements in clinical outcomes regarding the anthropometric variables of the child, the level of physical activity, psychological distress, and eating disorder of the child, after both interventions (ENTREN and ENTREN-F programme), in comparison to control group (d) There will be only improvements in clinical outcomes regarding in the family's healthy life-style, psychological distress of the parents, and the family environment, after the intervention of the ENTREN-F programme. (e) The significant changes produced will remain stable at the 6, 12 and 18-month follow-up in the ENTREN-F group.

Method

Participants and Recruitment Procedure

The sample will be made up of 240 children of 8-12 years old (IMC>P90). The dropout rate is expected to be 20%. The majority of the participants will be recruited through Primary Health Care Services, in collaboration with Pediatrics Area. Another percentage of the sample contacted the program after receiving information from their school or advertising posters.

Participation was voluntary and informed assent and consent was obtained by each participating family. Participants were told that the personal content of session discussions was confidential and should not be discussed outside the sessions.

Participants were randomly assigned to either (a) the psychofamily-based workshop program (ENTREN-F), (b) the only psychological workshop program (ENTREN) or (c) the Control Group. Participants were asked to complete questionnaires at baseline prior to the intervention (T_0) , at the end of the intervention and (T_1) , at 6-month follow-up (T_2) , at 12-month follow-up (T_3) and at 18-month follow-up (T_4) .

Design and contents

ENTREN Programme (experimental)

This intervention consists in a total of 12 biweekly sessions: 9 sessions of 2-hr only for children, with a further three 3-hr sessions attended by both families and children together: nutrition, physical activity sessions, and a closing event session. Los contenidos

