## **Statistical Analysis Plan (SAP)**

The statistical considerations for analyzing the data collected in the study are detailed below:

First, analyses will be carried out with the SPSS 26.0 version (IBM, SPSS, 2019).

Descriptive statistics (means, standard deviations, and percentages) of all the sociodemographic, clinical, and psychological variables will be calculated. A Shapiro–Wilk test will be used to check normal distribution.

Participant BMI changes over time by group will be measured using a Kruskal-Wallis test.

To carry out the comparisons, two-way analysis of covariance (ENTREN-F, ENTREN, Control Group) and time (T0,T1, T2 and T3) will be used.

Mixed model repeated measures analyses of covariance models tested whether intervention effects varied for each type of group.

In those cases in which we found significance in the global comparisons, we will carried out pairwise comparisons following asignificant main effect of time (post hoc Bonferroni test).

Finally, the effect size will be measured using partial eta squared ( $\eta$ 2), which estimates the degree of association for the sample. The guidelines for interpreting this value are as follows:  $\geq$ 0.14, large effect;  $\geq$ 0.06, medium effect;  $\geq$ 0.01, small effect (Cohen, 1988). The value P<0.05 was considered as a significant difference.

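### With 192 to 240 children, a null group or group-by-time effect reaches the SAP's 0.01 'small effect' cut-off for partial eta squared in about 30–46% of tests, and no adjusted between-arm difference is named

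*SAP*

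**What the plan says.** The SAP names one effect-size measure for the whole trial: "the effect size will be measured using partial eta squared", "which estimates the degree of association for the sample". It then gives cut-offs of 0.14 for large, 0.06 for medium and 0.01 for "small effect (Cohen, 1988"). No bias-corrected version and no confidence interval is mentioned.

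The model to which the measure belongs is a "two-way analysis of covariance (ENTREN-F, ENTREN, Control Group) and time (T0,T1, T2 and T3) will be used", followed by repeated-measures mixed models. BMI change by group is assigned to a Kruskal-Wallis test. Pairwise comparisons are made only after a significant global comparison. The effect-size paragraph opens separately and carries no such condition; its closing sentence is "The value P<0.05 was considered as a significant difference".

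On size, the Protocol (Participants and Recruitment Procedure) says "The sample will be made up of 240 children of 8-12 years old" and "The dropout rate is expected to be 20" per cent. It does not say whether 240 is before or after dropout.

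**The concern.** Partial eta squared computed from a sample cannot be negative, so chance differences between arms always push it above zero. How far depends on the degrees of freedom. If the lowest cut-off lies near the value that chance alone produces, the label 'small effect' does not separate an effect from none.

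There is a second gap. The Protocol's hypotheses are about particular arms: both programmes against control for the child outcomes, and gains in the family outcomes with ENTREN-F only. An omnibus variance-explained figure has no direction and does not show which arms differ. A Kruskal-Wallis test does not produce it either, so the test named for BMI has no matching effect size. At stake is how results are described across a long list of child and parent scales, and whether a reader can see how large any between-arm difference is.

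**Working it through.** The documents give no target effect, SD or power for the 240, so there is no stated calculation to reproduce.

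**Inputs**
- Three arms (SAP), so the group effect has 2 df.
- Four time points, T0 to T3 (SAP), so group by time has 2 × 3 = 6 df.
- N = 240 (Protocol), or 240 × 0.8 = 192 if 240 is the number enrolled and only children with complete data are analysed. The second reading is an assumption.
- Label cut-off 0.01 and alpha 0.05 (SAP).
- No covariate and sphericity, as the simplest case; both are varied below.

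**Formulas.** Under no effect, partial eta squared = df1·F/(df1·F + df2) follows a Beta(df1/2, df2/2) distribution. Write b = df2/2 and c = 0.01.
- Mean: df1/(df1 + df2).
- Chance of reaching c with df1 = 2: (1 − c)^b.
- Chance of reaching c with df1 = 6: (1 − c)^b × [1 + bc + b(b + 1)c²/2].
- Value needed for p = 0.05 with df1 = 2: 1 − 0.05^(2/df2). With df1 = 6 it comes from the F quantile.

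**N = 192**
- Group, df 2 and 189: mean 2/191 = 0.0105; chance 0.99^94.5 = 0.387.
- Group by time, df 6 and 567: mean 6/573 = 0.0105; chance 0.99^283.5 × (1 + 2.835 + 4.033) = 0.0579 × 7.868 = 0.455.

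**N = 240**
- Group, df 2 and 237: mean 2/239 = 0.0084; chance 0.99^118.5 = 0.304.
- Group by time, df 6 and 711: mean 6/717 = 0.0084; chance 0.99^355.5 × (1 + 3.555 + 6.337) = 0.0281 × 10.892 = 0.306.

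| Effect | N | Null mean | Chance of at least 0.01 | Value at p = 0.05 |
|---|---|---|---|---|
| Group | 192 | 0.0105 | 38.7% | 0.031 |
| Group | 240 | 0.0084 | 30.4% | 0.025 |
| Group by time | 192 | 0.0105 | 45.5% | 0.022 |
| Group by time | 240 | 0.0084 | 30.6% | 0.0175 |

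So any group value from 0.01 up to 0.025–0.031, or group-by-time value from 0.01 up to 0.0175–0.022, is non-significant and still meets the stated description of small.

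**Sensitivity**
- One covariate changes the chances by less than half a percentage point.
- Departure from sphericity (epsilon 0.5 to 0.85) gives 41–45% for group by time at N = 192 and 31% at N = 240.
- The Protocol also schedules a fifth assessment ("at 12-month follow-up (T_3) and at 18-month follow-up (T_4")). With five time points, group by time gives 47% at N = 192 and 30% at N = 240.
- Simulation with 10,000 replicates per case, under compound symmetry and AR(1), gives 38–39% (group) and 42–45% (group by time) at N = 192, and 29–31% for both at N = 240.

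**Where the figures do not apply**
- One-df pairwise contrasts: 12–21% at N = 240 and 17–26% at N = 192, depending on whether the error term is pooled over three arms or taken from two.
- Time main effect, four visits: 7% at N = 240 and 13% at N = 192.
- The 0.06 cut-off is reached by a null group or group-by-time effect in 0.3% of tests or fewer, so the medium and large labels are not in question.

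**The case against.** The strongest reply is that the labels are a cited convention for interpretation and decide nothing. P<0.05 is the only decision rule, and it stands in the same paragraph. If the sponsor attaches labels only to significant results, at most 5% of null tests would be labelled. This stands in part: the consequence is descriptive, and no test or sample size changes. But the SAP does not write that restriction. Its significance condition governs the pairwise comparisons, not the effect size.

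Three stronger readings are tempting, and the documents do not support them.
- A reader might infer that 0.01 equals the null expectation at this sample size, so that about four in ten of all null comparisons would be labelled. That needs about 192 complete cases and the three-arm omnibus tests. The SAP does not define 192 as an analysis set or require complete-case deletion. The null mean for the group effect is exactly 0.01 only at N = 2/0.01 + 1 = 201, and with all 240 analysed it is 0.0084.
- A reader might infer that noise will be reported as benefit. A measure without direction cannot by itself show benefit for any arm, and how the labels will be used is a prediction.
- A reader might infer that the BMI difference between arms will never be estimated. The SAP plans means and standard deviations of the clinical variables and does not exclude BMI from the covariance models. What is absent is narrower: no adjusted between-arm difference with a confidence interval is named.

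**Conclusion.** The point holds within limits. For the group and group-by-time tests, which carry the treatment question, the 0.01 cut-off lies close to what chance alone produces: expected value 0.008–0.0105, and 30–46% of null tests at or above the cut-off with the SAP's four time points. The low end assumes all 240 children are analysed, the high end 192 complete cases. Both assume that labels are given whatever the p-value, which the SAP leaves open.

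Separately, and whatever the cut-off, an omnibus measure cannot answer the arm-specific hypotheses. This is a cheap improvement to reporting and not a threat to the trial's conclusions.

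**What to change.** Make adjusted mean differences with 95% confidence intervals the main effect measure: ENTREN-F vs control, ENTREN vs control, and ENTREN-F vs ENTREN, at each post-baseline visit. Give them in scale units (BMI z-score for BMI) and also divided by the baseline SD.

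If a variance-explained measure is kept beside them, use a bias-corrected one (partial omega squared or partial epsilon squared) with its confidence interval. State that no verbal label is given when the corresponding test is not significant.

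This needs no new data. It costs a few sentences in the SAP and a changed table layout. The downside is that three contrasts per outcome and visit replace a single summary value.
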